7.5 Duration of Study Therapy

Arm 1 (high-risk aGVHD): Study treatment will be for a minimum of 7 days with study therapy continuing for an additional 5 weeks if a complete or partial response is documented at the initial response evaluation. Non-responders at 7 days will be taken off study therapy and treated at the discretion of the treating physician. The treating physician may remove patients from study participation sooner if concerns regarding safety emerge prior to completing 7 days on protocol.

Arm 2A and 2B (steroid-refractory/dependent aGVHD): Study treatment will be for a minimum of 14 days with study therapy continuing for an additional 5 weeks if a complete or partial response is documented at the initial response evaluation. Non-responders at 14 days will be taken off study

therapy and treated at the discretion of the treating physician. The treating physician may remove patients from study participation sooner if concerns regarding safety emerge prior to completing 14 days on protocol.

An exception to the above is if a patient experiences an event that fits the definition of a dose limiting toxicity (Grade 2-4 thromboembolic event, Grade 3-4 ascites or Grade 3-4 ovarian hyperstimulation syndrome). Study treatment will be permanently discontinued in this situation.

7.6 Duration of Study Participation

All participants will be followed for adverse events through day 56, or if a non-responder at initial assessment; for 28 days after the last dose of Pregnyl® to rule-out early thromboembolic events. The remainder of follow up data for study endpoints will coincide with routine transplant related follow-up (chart review database query).

8 Study Drug Formulation, Preparation, Side Effects

8.1 Human Chorionic Gonadotropin (HCG) (Pregnyl® (Merck), or generic urinary-derived hCG from Fresenius Kabi)

Pregnyl® or its generic equivalent (chorionic gonadotropin for injection USP) is a highly purified pyrogen-free preparation obtained from the urine of pregnant females.

Complete prescribing information for urinary HCG can be located at the following internet address:

http://www.accessdata.fda.gov/drugsatfda_docs/label/2011/017692s021lbl.pdf

PROCUREMENT: Pregnyl® or its generic equivalent will be purchased from a commercial source for the purposes of this study.

DOSAGE AND ADMINISTRATION: This drug is currently licensed by the FDA for intramuscular use only. However, in clinical practice, it is commonly given subcutaneously. Because of the risk of bleeding due to IM injections, and because of the otherwise off-label use for this drug, we have sought an IND from the FDA to administer Pregnyl® or its generic equivalent via subcutaneous route during this clinical trial.

PREPARATION: The drug is supplied in two-vial package containing:

1. 1-10 mL lyophilized multiple dose vial containing: 10,000 USP Units chorionic gonadotropin per vial, NDC 0052-0315-10 (Pregnyl) or NDC 63323 (Fresenius Kabi).
2. 1-10 mL vial of solvent containing: water for injection with sodium chloride 0.56% and benzyl alcohol 0.9%, NDC 0052-0325-10 (Pregnyl) or NDC 63323 (Fresenius Kabi).

Each lot of Pregnyl® or its generic equivalent will be tested for EGF content prior to administration so that the precise EGF dose administered is known.

When reconstituted, each 10 mL vial contains:

- Chorionic gonadotropin 10,000 USP Units
- Monobasic sodium phosphate 5 mg
- Dibasic sodium phosphate 4.4 mg
- Sodium chloride 0.56%
- Benzyl alcohol 0.9%

If required pH adjusted with sodium hydroxide and/or phosphoric acid.

NOTE: For Arm 2B, Dose level 5, in order to avoid using vials from more than one Lot of study product, the maximum dose is either (1) the contents of a single 10,000 IU vial, or (2) a maximum dose of 10,000 IU from multiple vials. All vials used should be from the same Lot.

IMPORTANT: RECONSTITUTED SOLUTION IS STABLE FOR 60 DAYS WHEN REFRIGERATED.

PRECAUTIONS

1. General: Since androgens may cause fluid retention, hCG should be used with caution in patients with cardiac or renal disease, epilepsy, migraine, or asthma.
2. Pediatric Use: Induction of androgen secretion by hCG may induce precocious puberty in pediatric patients treated for cryptorchidism. Therapy should be discontinued if signs of precocious puberty occur.
3. Geriatric Use: Clinical studies of PREGNYL® (chorionic gonadotropin for injection, USP) and its generic equivalent did not include subjects aged 65 and over.
4. ADVERSE REACTIONS: Headache, irritability, restlessness, depression, fatigue, edema, precocious puberty, gynecomastia, pain at

the site of injection. Hypersensitivity reactions, both localized and systemic in nature, have been reported.

9 Disease Reassessment and Response Definitions

Participants will be staged according to the Minnesota grading schema below:

GUIDE FOR GVHD STAGING

ORGAN	CLINICAL STAGE	
SKIN	1 = Rash <25% BSA	
	2 = Rash 25-50% BSA	
	3 = Generalized erythroderma	
	4 = Generalized erythroderma with bullous formation or desquamation	
LOWER GI	ADULT	PEDS
	0 = <500	(<280ml/m ²)
	1 = 500-1000	(281-555ml/m ²)
	2 = 1000-1500	(556-833ml/m ²)
	3 = >1500	(>834ml/m ²)
	4 = Severe abdomen pain with or without ileus, or stool with frank blood	
Liver	1 = Bili 2.1-3.0	
	2 = Bili 3.1-6.0	
	3 = Bili 6.1-15.0	
	4 = Bili >15.1	
UPPER GI	0 = No prolonged nausea or vomiting	
	1 = Persistent nausea, vomiting or anorexia	

Overall Grade	Organ Stage			
	Skin	Liver	Lower GI	Upper GI
I	1-2	0	0	0
II	3	1	1	1
III	-	2-4	2-3	
IV	4	-	4	

Response will be based on the following definitions:

- **Complete Response (CR):** a Stage of 0 for all organs with no additional intervening therapy for their GVHD.
- **Partial Response (PR):** improvement by at least 1 stage in all involved organs without progression in others with no additional intervening therapy for their GVHD.
- **Mixed Response (MR):** improvement in one organ with deterioration in another organ manifesting symptoms of GVHD or development of symptoms of GVHD in a new organ.
- **Progression:** deterioration of any organ involved.

- **No Response (NR):** absence of any improvement or progression as defined above.

10 Schedule of Patient Activities

Scheduled evaluations after screening and through day 19 of the last treatment cycle may be performed +/-2 days from the targeted date; assessments performed after day 28 and through day 56 may be done +/-5 days of the targeted date. After day 56, assessments will coincide with the post-transplant follow-up schedule (i.e., additional clinic visits specifically for this study will not be required). In addition, targeted days may be altered as clinically appropriate, and will not constitute a protocol deviation.

Schedule of Treatment, Tests and Procedures – Arm 1

	Baseline	Treatment Days +/- 2 days												Phase I only	Follow Up +/- 5 days***	
Procedures, evaluations, and treatment		1	3	5	7	9	11	13	14	15	17	19		21	28	56
Standard of Care																
Vital signs and weight	X	X	X	X	X	X	X	X	X	X	X	X			X	X
Performance status (Karnofsky or Lansky)	X				X				X			X			X	X
Acute GVHD staging	X				X				X						X	X
Complete blood count	X				X				X			X			X	X
Complete metabolic panel	X				X				X			X			X	X
Serum creatinine	X															
Ejection Fraction by echocardiogram or MUGA	X															
Research																
Pregnyl® dosing*		X	X	X	X	*										
Assess for toxicity		beginning with the 1st dose of Pregnyl® and continuing for 4 weeks after the last dose per section 11.2 (if phase I assess for DLT at day 21)														
Pharmacokinetics**		X			X											
Serum hCG	X^				X				X						X	X
Estradiol, progesterone, and testosterone	X				X				X						X	X
Collection of blood samples for immune and tissue damage/repair biomarkers (refer to section 10.3 for blood volume and tube type)s	X				X				X						X	X

MT2014-12: hCG supplementation in high-risk or refractory aGVHD

Research related blood samples will go to Translational Therapy Lab (TTL) for processing and storage until study related testing.

*If a patient achieves a complete or partial response, he/she may continue to receive maintenance Pregnyl® doses twice per week, in the dose level he or she was already assigned, for another 10 doses, beginning during protocol day 9-12.

**Blood samples (2 ml plasma) collected 30 (\pm 10) minutes pre-dose, and at post-dose 1 hour (\pm 5 min), 3 hours (\pm 5 min), 6 hours (\pm 10 min), and 24 hours (\pm 30 min).

***After day 56 endpoint assessments will coincide with the post-transplant anniversary visits and the information may be abstracted from the medical record and/or the BMT database.

[^] testing to rule-out pregnancy will be performed on females for eligibility screening

Schedule of Treatment, Tests and Procedures – Arm 2

	Baseline	Treatment Days +/- 2 days												Phase I only	Follow Up +/- 5 days***	
		1	3	5	7	9	11	13	14	15	17	19	21		28	56
Standard of Care																
Vital signs and weight	X	X	X	X	X	X	X	X	X	X	X	X		X	X	
Performance status (Karnofsky or Lansky)	X				X					X			X		X	X
Acute GVHD staging	X				X					X			X		X	X
Complete blood count	X				X					X			X		X	X
Complete metabolic panel	X				X					X			X		X	X
Serum creatinine	X															
Ejection Fraction by echocardiogram or MUGA	X															
Research																
Pregnyl® dosing*		X	X	X	X	X	X	X		*						
Assess for toxicity		beginning with the 1st dose of Pregnyl® and continuing for 4 weeks after the last dose per section 11.2 (if phase I assess for DLT at day 21)														
Pharmacokinetics**		X							X							
Serum hCG	X [^]				X					X					X	X
Estradiol, progesterone, and testosterone	X				X					X					X	X
Collection of blood samples for immune and tissue damage/repair biomarkers (refer to section 10.1 for blood volume and tube type)	X				X					X					X	X

Research related blood samples will go to Translational Therapy Lab (TTL) for processing and storage until study related testing.

*If a patient achieves a complete or partial response, he/she may continue to receive maintenance Pregnyl® doses twice per week, in the dose level he or she was already assigned, for another 10 doses, beginning during protocol day 15-17.

**Blood samples (plasma) collected 30 (\pm 10) minutes pre-dose, and at post-dose 1 hour (\pm 5 min), 3 hours (\pm 5 min), 6 hours (\pm 10 min), and 24 hours (\pm 30 min).

***After day 56 endpoint assessments will coincide with the post-transplant anniversary visits and the information may be abstracted from the medical record and/or the BMT database.

[^] testing to rule-out pregnancy will be performed on females for eligibility screening

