7.1 Arm 1 – High-Risk aGVHD

Standard of care immunosuppression, plus Pregnyl® (hCG supplementation) at assigned dose subcutaneously every other day for 4 doses

If a patient has a toxicity that fits the definition of dose limiting as defined in the phase I section below, the patient will discontinue study treatment.

Continue protocol treatment through day 7. Assess response at day 7:

- **If a complete or partial response**, the patient is eligible to receive Pregnyl maintenance at the same dose twice weekly for 10 doses beginning day 9 to 12. Refer to [section 9](#) for response definitions.
- **If no response**, the patient will be taken off study treatment

Pregnyl® dose level assignment will be done by treatment arm, with Arm 1 independent of Arms 2A and 2B.

For phase I, up to 5 dose levels of Pregnyl® will be tested; however dose levels -1 and -2 will be used only if dose level 1 proves too toxic.

Dose Level	Dose
-2	125 USP hCG/875 pg EGF/m ²
-1	250 USP hCG/1,750 pg EGF/m ²
1 (start)	500 USP hCG/3,500 pg EGF/m ²
2	1,000 USP hCG/7,000 pg EGF/m ²
3	2,000 USP hCG/14,000 pg EGF/m ²

The 1st 2 patients will be enrolled in dose level 1. The next cohort of 2 patients will not begin treatment until all patients in the current cohort have reached day 21 in order to assess for dose limiting toxicity (DLT).

Dose limiting toxicity (DLT) is defined as any of the following occurring by day 21 after the 1st dose of Pregnyl® (phase I component only):

- In males and females: Grade 2-4 thromboembolic event (CTCAE v4) i.e., any thrombosis more severe than a superficial venous thrombosis develops and treatment with anticoagulation is required
- In males and females: Grade 3-4 ascites (CTCAE v4)
- Specific to females: Grade 3-4 ovarian hyperstimulation syndrome, defined as the rapid development of enlarged, cystic, painful ovaries - refer to [section 11.2](#) for CTCAE grading guidance

Each new cohort of 2 patients will be assigned by the study statistician to the most appropriate dose level based on toxicity probabilities set for this study. The MTD will be identified when the total sample size of 20 patients is reached.

For the phase II the dose of Pregnyl will be that identified as the MTD during phase I.

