11.2 Adverse Event Documentation

Due to the complex medical condition of the post-transplant patient, monitoring for adverse events will focus on the following events beginning with the 1st dose of Pregnyl® and continuing for 4 weeks after the last dose. Any of these events will be documented on the study specific case report form:

- death
- anaphylaxis
- thromboembolic event
- Grade 3-4 skin injection site reaction
- Grade 3 headache
- Grade 3 gynecomastia
- Grade 3-4 ascites

In addition, the following events occurring by day 21 after the 1st dose of Pregnyl® are considered a dose limiting toxicity (DLT) and should be reported as such for patients enrolled in the Phase I component per [section 11.4](#):

- In males and females: Grade 2-4 thromboembolic event (CTCAE v4)
- In males and females: Grade 3-4 ascites (CTCAE v4)
- Specific to females: Grade 3-4 ovarian hyperstimulation syndrome, defined as the rapid development of enlarged, cystic, painful ovaries, Note: as there is no CTCAE grading for this event, the generic grading will apply as follows:

Grade	Description
1	mild; asymptomatic or mild symptoms; clinical or diagnostic observations
2	moderate; minimal or non-invasive intervention indicated

Grade	Description
3	severe or medically significant but not immediately life-threatening; hospitalization or prolongation of hospitalization indicated
4	life-threatening consequences; urgent intervention indicated

For the Phase II expansion cohort, an early study stopping rule was developed for excessive Grade 4/5 non-hematologic, non-infectious treatment probably or definitely attributed to the study drug occurring by day 28 after the last dose of Pregnyl® and is reportable per [section 11.4](#). Refer to [section 13.4](#) for details.

For both cohorts, relapse of the patient's malignancy and/or development of a new one occurring 4 weeks after the last dose is reportable per [section 11.4](#).

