11.3 Institutional Event Reporting Table

Individual institutional sites will be responsible for reporting any event meeting local reporting requirements to their institutional IRB and/or other research oversight committees.

Additionally institutional sites will be responsible for reporting events detailed in [sections 11.1](#) and [11.2](#) within the following time frames to the MCC Affiliate Sites Manager

Event Type	Reporting Timeframe	Form in OnCore to Use	Report to
Any event meeting the definition of a SAE within 4 weeks after last dose of pregnyl	Within 24 hours of knowledge	SAE Report Form	Masonic Cancer Center (MCC) Affiliate Sites Manager [contact] Local institutional IRB or other entities per institutional policies and guidelines.
Event counting toward the safety stopping rule as defined in Section 13.4	Within 24 hours of knowledge	Stopping Rule Event Form	
Major Deviations, as defined in Section 11.1 .	Within 5 working days of knowledge	Deviation Report Form	
Minor Deviations, as defined in Section 11.1 .	Per Institutional Policy	n/a (record in Deviations Tab) but it is not necessary to report the event to MCC	For UMN MCC only: minor deviations are reported to the UMN IRB by the study's regulatory specialist per IRB reporting requirements. For Affiliate Sites: minor deviations are not reportable to the Masonic Cancer Center. Report to local institutional IRB or other entities per institutional policies and guidelines.

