13.4 Early Stopping Rule

During Phase I CRM, the trial will stop if the posterior probability that the lowest dose is more toxic than the target is greater than 90%. Stopping rules will also be employed to monitor excess toxicity outside of the phase I trial. Stopping rule was developed using Pocock stopping boundaries [32]. The stopping rule will be monitored for Arm 1, 2A and Arm 2B separately.

Early Stopping Rule for Toxicity

Stopping rules were developed for excessive Grade 4/5 non-hematologic, non-infectious toxicity attributed to the study drug occurring by day 28 after the last dose of hCG. The goal is to construct a boundary based on toxicity such that the probability of early stopping is at most 10% if the toxicity rate is equal to 20% and assuming 13 more patients of each arm are enrolled after phase I. Given these parameters, the upper stopping boundary for toxicity is 2 events out of 2 patients, 3 events out of 3 patients, 5 out of 8, or 6 at any time. If the true toxicity rate is as high as 50% then chance of early stopping is 80% and the expected sample size is 7.3.

14 Conduct of the Study

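### Section 7.6 ends responders' adverse-event follow-up at day 56, but the safety and stopping-rule sections run to 28 days after the last dose, about day 68–77

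*Combined protocol and SAP*

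**What the plan says.** Section 7.6 (Duration of Study Participation) states: "All participants will be followed for adverse events through day 56, or if a non-responder at initial assessment; for 28 days". For non-responders the 28 days are counted from the final Pregnyl dose, and the reason given is to exclude early thromboembolic events. Its next sentence leaves the remaining endpoint data to routine transplant follow-up and chart review.

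The other safety passages count from the last dose and make no exception for responders:

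- Section 11.2 monitors the targeted events "beginning with the 1st dose of Pregnyl® and continuing for 4 weeks after the last dose". It also restates the phase II stopping-rule window as 28 days after the last dose.
- The toxicity row of both schedules in section 10 reads "beginning with the 1st dose of Pregnyl® and continuing for 4 weeks after the last dose per section 11.2".
- The first row of the table in section 11.3 covers "Any event meeting the definition of a SAE within 4 weeks after last dose of pregnyl".
- Section 13.4 counts Grade 4/5 non-hematologic, "non-infectious toxicity attributed to the study drug occurring by day 28 after the last dose of hCG".
- Section 11.2 also covers relapse or "development of a new one occurring 4 weeks after the last dose is reportable per" section 11.4. This sentence is looser, because it does not say whether it means within 4 weeks.

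On maintenance, section 7.1 says of those who have responded by day 7: "the patient is eligible to receive Pregnyl maintenance at the same dose twice weekly for 10 doses beginning day 9 to 12". Sections 7.2 and 7.3 give Arms 2A and 2B the same course starting on day 15 to 17. Section 10 says that after day 56 "additional clinic visits specifically for this study will not be required".

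**The concern.** Two different end points are given for the same safety observation, and no passage says which governs. The difference matters only for responders, because only they receive doses late enough for 28 post-dose days to run past day 56. They are also the patients with the most doses: 4 + 10 = 14 in Arm 1 and 7 + 10 = 17 in Arms 2A and 2B.

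A site could reasonably take 7.6 as its instruction. It is the section on duration of participation, the last column of each schedule is day 56, and no study visit is required afterwards. The chart review in 7.6 is for endpoint data and does not mention adverse events.

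A site that stopped looking at day 56 could miss late non-fatal targeted events, such as thromboembolism or ascites, and Grade 4 events that count under 13.4. That boundary is a small count (2 of 2, 3 of 3, 5 of 8, or 6 at any time), so one unrecorded event can decide whether it is crossed. Missing events can only lower the count.

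**Working it through.** **Inputs.** Maintenance is 10 doses, twice weekly, starting on day 9–12 in Arm 1 (7.1) or day 15–17 in Arms 2A and 2B (7.2, 7.3). Initial dosing is on days 1, 3, 5 and 7 in Arm 1, and on days 1 to 13 every other day in Arm 2 (schedules, section 10). The limit in 7.6 is day 56. The window elsewhere is 28 days after the last dose.

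**The plan's own figure.** Section 7.5 gives maintenance as a further 5 weeks. 10 doses ÷ 2 per week = 5 weeks, so it reproduces.

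**Last maintenance dose.** I take twice weekly as alternating gaps of 3 and 4 days. Ten doses have 9 gaps: 5×3 + 4×4 = 31 days, or 5×4 + 4×3 = 32 days.

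| | Arm 1 | Arms 2A/2B |
|---|---|---|
| Start of maintenance | day 9–12 | day 15–17 |
| Last dose (start + 31 or 32) | day 40–44 | day 46–49 |
| End of window (last dose + 28) | day 68–72 | day 74–77 |
| Beyond day 56 | 12–16 days | 18–21 days |
| Share of the 28 days not covered | 12/28 = 43% to 16/28 = 57% | 18/28 = 64% to 21/28 = 75% |
| Post-dose days observed by day 56 | 56−44 = 12 to 56−40 = 16 | 56−49 = 7 to 56−46 = 10 |

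**Cross-check with the 5 weeks in 7.5.** Arm 1: 7 + 35 + 28 = day 70. Arms 2A/2B: 14 + 35 + 28 = day 77. Both fall within the ranges above.

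**Where the shortfall begins.** Day 56 covers 28 post-dose days only if the last dose is on or before 56 − 28 = day 28. The first maintenance dose after day 28 is dose 6 or 7 in Arm 1 (day 29–32) and dose 5 in Arms 2A/2B (day 29–31). A responder who stops maintenance before that is fully covered.

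**Non-responders.** With all initial doses given, the last dose is on day 7 (Arm 1) or day 13 (Arm 2). The windows end on day 7 + 28 = 35 and day 13 + 28 = 41. For them 7.6 and 11.2 agree.

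**Visit tolerance, kept separate.** The day-56 visit may fall on day 51–61. From that visit to the end of the window is 68−61 = 7 to 72−51 = 21 days in Arm 1, and 74−61 = 13 to 77−51 = 26 days in Arms 2A/2B. This spread comes from the ±5 days in section 10. The part caused by 7.6 is 12–16 and 18–21 days.

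**The case against.** The strongest reply is that the operative safety passages already require the longer window. The schedules send sites to 11.2 and not to 7.6. Section 11.3 requires SAEs within that window, and stopping-rule events, to be reported within 24 hours of knowledge whatever 7.6 says. On this view 7.6 is one badly punctuated sentence, and its day 56 may be meant as a minimum. Deaths and relapses would still be found through the survival and disease-free survival follow-up. What could be lost is then narrow: non-fatal events after day 56 that nobody learns of.

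Most of this is fair and limits the consequence. It does not remove the conflict. 7.6 separates responders from non-responders explicitly, so its day 56 reads as the responders' period, and nothing gives 11.2 precedence. A duty to report within 24 hours of knowledge does not make anyone look. The effect in 7.6 is also the reverse of its stated purpose: a non-responder with 4 or 7 doses is watched for 28 post-dose days, and a responder who completes 14 or 17 doses for 7–16.

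Two further objections stand in part. The relapse and new-malignancy sentence in 11.2 is ambiguous and adds little. The number of events at stake may also be small: section 2 puts severe reactions such as arterial thromboembolism and ovarian hyperstimulation below 1%, and section 13.2 reports no DLT in 10 + 4 + 7 = 21 treated patients. Those DLTs, however, cover only the first 21 days and say nothing about the period after day 56.

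**Conclusion.** The concern holds: 7.6 contradicts 11.2, 11.3, 13.4 and both schedules. For a responder who completes maintenance, 7.6 falls 12–16 days short in Arm 1 and 18–21 days short in Arms 2A/2B. This rests on twice-weekly dosing at 3- and 4-day gaps with all 10 doses given on schedule; the ±2-day treatment windows can shift the dates slightly.

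The contradiction is certain, but the loss is conditional on sites following 7.6. Phase I DLTs (day 21) and non-responders are not affected.

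The share of patients affected is unknown, because maintenance is optional and depends on response at day 7 or 14, for which no rate is given. Purely as an assumption, suppose the share completing maintenance equalled the day-28 planning rates of 40% to 65%. Of the 13 further patients per arm assumed in 13.4, 0.40×13 = 5.2 to 0.65×13 = 8.45 would then be affected. Day-28 response is a different quantity, so this is not an estimate.

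The passages should be reconciled. Nothing here puts the design or the dosing in question.

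**What to change.** Reword the follow-up sentence in 7.6 so that adverse-event follow-up runs to at least 28 days after the last dose of Pregnyl for every participant, in line with 11.2, 11.3, 13.4 and the schedules. Keep the day-56 visit for responders, and leave non-responders' follow-up as it is. For responders whose window runs past day 56, state that the targeted events in 11.2 and the stopping-rule events in 13.4 are collected at routine post-transplant contacts or by chart review. Chart review should be named, because the anniversary visits used for later endpoints need not fall between day 56 and day 77.

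The cost is one sentence in 7.6 and, for each responder who completes maintenance, 12–16 (Arm 1) or 18–21 (Arms 2A/2B) more days of targeted-event abstraction. No study visit is added, and nothing extra is needed for non-responders.
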